4. ADVERSE EVENT MANAGEMENT

4.1 Definitions

4.1.1 Adverse Events (AE)

An Adverse Event (AE) is defined as any untoward medical occurrence involving a participant, which does not necessarily have a causal relationship with the intervention or study.

4.1.2 Serious Adverse Events (SAEs)

A SAE is any untoward medical occurrence that fulfils one or more of the following criteria:

- Results in death
- Is immediately life-threatening
- Requires hospitalisation or prolongation of existing hospitalisation
- Results in persistent or significant disability or incapacity
- Is a congenital abnormality or birth defect
- Intervention is required to prevent one of the above or is an important medical condition

4.2 Recording Adverse Events and Reporting Serious Adverse Events

4.2.1 Recording and reporting period

Intervention group: All AEs and SAEs that occur during or within 24 hours of a REGAIN live online session or an on-demand exercise session (supervised or unsupervised) should be recorded on the AE log by the exercise practitioner.

Usual care group: The usual care group will be asked about anything that might constitute a Serious Adverse Event at the time of their three-month follow-up. It will not be possible to collect a comparison dataset for the usual care group within this period without contaminating the control intervention. This is a pragmatic study and the participants will not be contacted during the intervention period, unlike the intervention group. It is important not to contact the usual care group more than is necessary so as not to introduce bias. We anticipate a low risk of adverse events arising from best practice usual care i.e. an NHS website and a single session of advice.

4.2.2 Recording Adverse Events

Participants in the intervention group will have the opportunity to indicate whether or not they have experienced AEs by completing both pre- and post-exercise session poll questions. Responses indicating the participant has potentially experienced an adverse event will be evaluated by the practitioner and the participant contacted to confirm the details. Practitioners should also monitor for any information volunteered by a participant at any time during a live exercise session. Participants in the intervention group will also have contact details (generic email address and phone number) for the study team and practitioners. Whilst participants will not be actively encouraged to report AEs via this route, they may seek advice and help from the team which may result in AEs being disclosed/discussed. Any AEs will be recorded on the AE log unless they fulfil the criteria for a 'Serious Adverse Event' in which case they will be reported to WCTU via the SAE form (see section 14.2.3 below).

4.2.3 Reporting Serious Adverse Events

All AEs should be assessed by the research practitioner to determine if they meet the criteria to be reported as a 'serious adverse event' as defined in section 4.1.2. If any of the adverse events meet this criteria, they will be reported to WCTU by emailing [contact] using the Serious Adverse Event form within 24 hours of becoming aware of it. If the 3 month questionnaire for a control group or REGAIN intervention group participant indicates events that may fulfil an SAE, then they should be contacted for further information and an SAE form completed if applicable.

A clinical assessment of whether the event has a causal relationship to the intervention should be made and recorded on the form by the practitioner. All SAEs should be reported irrespective of their relationship to the intervention unless they are exempt from reporting (see section 4.2.3.1).

For each **SAE** the following information will be collected:

- full details in medical terms and case description using CTCAE V5.0
- event duration (start and end dates, if applicable)
- action taken
- outcome
- seriousness criteria
- causality (relatedness to intervention), in the opinion of the practitioner
4.2.3.1 SAEs that are exempt from reporting

The following events that would usually fulfil the criteria for 'serious' do not need to be reported as per section 1.2.3:

- Treatment, which was elective or pre-planned, for a pre-existing condition, not associated with any deterioration in condition
- General care, not associated with any deterioration in condition

4.2.4 Determination of causality and expectedness for SAEs

Two independent causality assessments will be performed (i.e. relationship to study intervention). The practitioner will submit an assessment of their clinical opinion on causality upon submission of the SAE report using the classifications in SAE table 2 below. The CI will then do a separate causality assessment on reported events on behalf of the sponsor. These two assessments should be independent of each other.

If either party suspect there is a possibility that the event is related to the intervention then a delegate on behalf of the Sponsor will assess whether or not this is expected using the information in 4.2.4.1 below. For any related and unexpected serious adverse events, WCTU will report this to the REC within 15 days of receipt.

4.2.4.1 Expected Serious Adverse Events

Due to the limited knowledge of the long-term health problems in COVID-19 survivors, there are no Serious Adverse Events that would be expected in exercise intervention for the population included in this study.

Relationship to study medication	Description	
Unrelated	There is no evidence of any causal relationship	
Unlikely to be related	There is little evidence to suggest there is a causal relationship (e.g. the event did not occur within a reasonable time after administration of the study intervention). There is another reasonable explanation for the event (e.g. the patient's clinical condition, other concomitant treatment).	
Possible relationship	ere is some evidence to suggest a causal relationship .g. because the event occurs within a reasonable time ter administration of the study intervention). owever, the influence of other factors may have ntributed to the event (e.g. the patient's clinical ndition, other concomitant treatments).	

Table 2. SAE Causal relationship

Probable relationship	There is evidence to suggest a causal relationship and the influence of other factors is unlikely.
Definitely related	There is clear evidence to suggest a causal relationship and other possible contributing factors can be ruled out.

4.2.5 Follow-up of reported SAEs

Practitioners will monitor for changes to unresolved SAEs via intervention poll responses or through close contact with the participant. If a practitioner becomes aware of any change of condition or other follow-up information it should be emailed to [contact] on the Serious Adverse Event Follow-Up form as soon as it is available or at least within 24 hours of the information becoming available. Events will be followed up until the event has resolved or a final outcome has been reached where possible.

4.3 Responsibilities

Practitioners:

Checking for AEs when participants attend for exercise session or via pre- and post-exercise poll responses:

- 1. Using clinical judgement in assigning seriousness and causality
- 2. Ensuring that all SAEs are recorded and reported to the Sponsor via Warwick QA within 24 hours of becoming aware of the event and provide further follow-up information as soon as available. Ensuring that reported SAEs are chased with WCTU if a record of receipt is not received within 2 working days of initial reporting.

Chief Investigator (CI) / delegate or independent clinical reviewer:

- 1. Clinical oversight of the safety of patients participating in the study, including an ongoing review of the risk / benefit.
- 2. Using clinical judgement in assigning causality
- 3. Immediate review of all related and unexpected SAEs
- 4. Review of specific SAEs in accordance with the study risk assessment and protocol as detailed in the Trial Monitoring Plan.
- 5. Production and submission of annual reports to the relevant REC.

Sponsor or delegate:

- 1. Central data collection and verification of SAEs, according to the study protocol.
- 2. Expectedness assessment of related SAEs
- 3. Reporting safety information to the CI, delegate or independent clinical reviewer for the ongoing assessment of the risk / benefit according to the Trial Monitoring Plan.
- 4. Reporting safety information to the independent oversight committees identified for the study (Data Monitoring Committee (DMC) and / or Trial Steering Committee (TSC)) according to the Trial Monitoring Plan.

- 5. Expedited reporting of related and unexpected SAEs to the REC within required timelines.
- 6. Notifying Investigators of related and unexpected SAEs that occur within the study.

Trial Steering Committee (TSC):

In accordance with the Trial Terms of Reference for the TSC, periodically reviewing safety data and liaising with the DMC regarding safety issues.

Data Monitoring Committee (DMC):

In accordance with the Trial Terms of Reference for the DMC, periodically reviewing unblinded overall safety data to determine patterns and trends of events, or to identify safety issues, which would not be apparent on an individual case basis.

4.4 Notification of deaths

All deaths, when they are identified, will be reported to the sponsor by the REGAIN practitioner, overseen by the CI, irrespective of whether the death is related to disease progression, the intervention, or an unrelated event.

Staff at the UHCW community exercise rehabilitation centre and WCTU may become aware of deaths that occur during the study however the majority of deaths will be identified by accessing GP records for those non-responders at 12 months post-randomisation.

4.5 Reporting urgent safety measures

If any urgent safety measures are taken the CI/Sponsor shall immediately and in any event no later than 3 days from the date the measures are taken, give written notice to the relevant REC of the measures taken and the circumstances giving rise to those measures.

5. DATA MANAGEMENT

Personal data collected during the study will be handled and stored in accordance with the General Data Protection Regulation and Data Protection Act 2018.

Personal identifying information will be collected on the online application and stored at WCTU for contacting the patient to: confirm eligibility and consent: complete and send a letter to the participants GP at baseline and at subsequent follow-up time points if one or more of HADS Anxiety sub-score, HADS Depression sub-score and IES-6 reveal possible case level mental health disorders; for intervention delivery (control and intervention arm); contact participants for follow up purposes; contact potential participants to take part in the interviews; and to request a copy of the participant's medical record from their GP. Information will be accessed via the online application by staff at UHCW (the community exercise rehabilitation centre) in order to contact the participants and deliver the study (intervention and control). Handling of personal and confidential data will be clearly documented in the participant information sheet and consent obtained.

Disclosure of confidential information will only be considered if there is an issue which may jeopardise the safety of the participant or another person, according to Warwick SOPs (Warwick

SOP 15 part 1) and the UK regulatory framework. There is no reason to expect this situation to occur in this study more than any other.

5.1 Data collection and management

The CRFs and questionnaires will be developed by the Trial Manager in consultation with the CI, Statistician, Health Economist and other relevant members of the study team to collect all required study data.

All data will be entered directly by participants, REGAIN practitioners or WCTU study team members onto a secure online study database hosted by WCTU as outlined in the data management plan and in accordance with the Warwick SOPs. Data entered onto the online study database will be source data. This will be stored safely and securely. Personal identifiable information will be stored separately to other data collection forms. On all study-specific documents, other than the signed consent, the participant will be referred to by the study participant number, not by name.

For SAE reports, anonymised paper CRFs may be completed by UHCW staff and returned via email to WCTU for data checking and quality assurance purposes by study team members at WCTU and Sponsor representatives at UHCW. The participant will be referred to by the study participant number/code, not by name. If printed these forms will be stored in locked filling cabinets within WCTU accessible only to authorised staff from the study team. Electronic data will be stored in a secure area of the computer with access restricted to staff working on the study.

Various methods will be used to chase missing data including phone, text and email. Participants will receive an email notification and/or text message to remind them to complete the online questionnaires at each follow-up time point. If a participant has not completed a follow-up questionnaire within the anticipated time frame, the REGAIN study team will initially contact the participant via telephone to encourage them to complete the missing data and to provide support where required. A link to the study database may be provided via email to facilitate data completion. If data remain missing following this initial data chase, the REGAIN study team will contact the participant after a pre-defined period of time via telephone in order to attempt to collect core outcome measurements only (PROPr and EQ5DL). Where necessary a bilingual researcher will assist with the collection of missing data from participants who are non-English speakers. The procedures for managing this will be outlined in the data management plan and appropriate consent will be sought to contact participants.

Data will still be collected for participants who discontinue or deviate from the intervention protocol, unless they withdraw their consent (section 2.9.2). For any participants who do not respond to the 12 month follow-up questionnaire, WCTU will request a copy of the participant's medical record from their GP. Identifiable data will be deleted within 6 weeks of completion of the study, specified as the point of withdrawal or completion of the 12 month follow-up questionnaire.

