Follow-up: Patient reported outcomes will be collected online at baseline pre-randomisation, three months, six months and 12 months post-randomisation. Participants will receive an email notification and/or text message to remind them to complete the online questionnaires at each follow-up time point. In the case of non-response, two key outcomes, the PROPr (primary outcome) and EQ-5D-5L will be collected by telephone. Fluency in English is not an inclusion criterion for this study. For those not fluent in English, we will aim to collect all outcomes (or as many as possible) verbally at each follow-up. As a minimum, a core data outcome set including the PROMIS® 29+2 Profile v2.1 (PROPr) and EQ-5D-5L questionnaires will be collected orally by a bilingual researcher, where necessary, to ensure that those not fluent in English are able to contribute participant reported outcomes to the study. The EQ-5D-5L is well validated for verbal administration.

Long-term follow-up: Consent will be sought from participants to hold their personal data, and at the end of the 12-month follow-up period, to request a copy of the participant's medical record from their GP. This will only be requested if the participant has not responded to the 12-month follow-up or if we know the participant has died. This will provide information on GP consultations and include copies of any hospital discharge letters allowing us to accurately cost in-patient care costs. Where appropriate, we will triangulate data from GP records and any participant self-report to achieve a robust estimate of health service activity and mortality.

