3. METHODS AND ASSESSMENTS

3.1 Schedule of delivery of intervention and data collection

Table 1. Study assessments

	Pre-randomisation		Post-randomisation				
Online assessment	1	2	3	4	5	6	
Assessment time point	Screening	Enrolment/ randomise (Baseline)	Intervention Delivery	3m (± 2w)	6 m (± 1 m)	12 m (± 1 m)	
Invitation letter and flyer posted	~						
Initial Eligibility Assessed	~						
Concomitant Illnesses		~					
Eligibility check* (telephone)		~					
Informed consent		~					
Patient Demographics		~					
Medication Use				~	✓	\checkmark	
PROMIS [®] 29+2 Profile v2.1 (PROPr)		~		~	~	✓	
PROMIS dyspnoea		~		~	√	~	
PROMIS Neuro- QoL		~		~	√	~	
EQ-5D-5L		✓		~	~	✓	
IPAQ-SF		✓		~	~	\checkmark	
IES-R		✓		~	~	\checkmark	
HADS		✓		~	~	\checkmark	
Work status		✓		~	~	\checkmark	
Intervention			✓				
Adverse events			✓				
Overall health		✓		~	~	\checkmark	
Death						\checkmark	
Health and Social Care resource use				✓	✓	~	

	Pre-rar	ndomisation	Post-randomisation				
Online assessment	1	2	3	4	5	6	
Assessment time point	Screening	Enrolment/ randomise (Baseline)	Intervention Delivery	3m (± 2w)	6 m (± 1 m)	12 m (± 1 m)	
Semi-structured interviews (Process evaluation)				~			

* Eligibility check will be performed in person over the telephone by clinical member of the research team at UHCW. All other assessments and information will be completed by the participant online.

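### English-fluent controls reached at three months only by the fallback telephone call have no planned enquiry about non-fatal serious adverse events

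*Protocol*

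**What the plan says.** **Controls.** Protocol 4.2.1 gives one enquiry: "The usual care group will be asked about anything that might constitute a Serious Adverse Event at the time of their three-month follow-up". Before that, "the participants will not be contacted during the intervention period, unlike the intervention group". Protocol 4.2.3 ties the enquiry to the form. Staff make contact "If the 3 month questionnaire for a control group or REGAIN intervention group participant indicates events that may fulfil an SAE".

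**Intervention arm.** It has the same three-month questionnaire, plus a log of "All AEs and SAEs that occur during or within 24 hours of a REGAIN live online session" or an on-demand session (Protocol 4.2.1). Polls before and after exercise sessions feed this log (4.2.2), and two consecutive missed appointments prompt a welfare contact (2.9.1).

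**Schedules.** In Table 1 of the Protocol (3.1) and of the SAP (2.10), the row "Adverse events" has one tick, under intervention delivery, and none at three, six or 12 months.

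**Non-response.** Protocol 5.1 has two steps. The team first "will initially contact the participant via telephone to encourage them to complete the missing data and to provide support where required". If data are still missing, the participant is later contacted "via telephone in order to attempt to collect core outcome measurements only (PROPr and EQ5DL"). Protocol 2.3.1 agrees: "In the case of non-response, two key outcomes, the PROPr (primary outcome) and EQ-5D-5L will be collected by telephone". SAP 2.6.2 names the same two measures.

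**Analysis.** SAP section 6 reports the frequency and percentage of SAEs by arm. It gives no denominator and says nothing about participants who were not asked.

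**The concern.** The final call is meant to rescue the primary outcome, and a participant reached that way counts as followed up. If the SAE enquiry is only on the online form, such a person enters the safety table with no recorded event when nobody has asked. Someone who was in hospital when the form fell due is a plausible example, so the unasked group may carry more events than the rest.

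The loss is not balanced in effect. An intervention participant who skips the form may already have been picked up through polls, practitioner monitoring or the welfare contact. A control participant has no equivalent route for a non-fatal event. Missing control events would lower the control SAE percentage and make the intervention look relatively worse on safety.

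**Working it through.** **1. The route for one control participant.** Take someone fluent in English who is admitted to hospital in month two and survives, does not complete the three-month form despite the first chase call, answers the final call, and completes the 12-month form.

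- During the intervention period: no contact (Protocol 4.2.1).
- Three-month questionnaire: not completed, so it cannot flag an event (4.2.3).
- Final call: PROPr and EQ-5D-5L only (5.1, 2.3.1; SAP 2.6.2).
- Resource-use questions: not in the call's core set, and no rule links them to SAE reporting.
- GP record: requested only after 12-month non-response or a known death (2.3.1, 3.2), so not requested here. Its discharge letters are obtained for costing.

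The plan contains no SAE enquiry for this person.

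**2. Size of the control arm.** The planned size reproduces. With a design effect of 1 + (8 - 1) x 0.01 = 1.07, allocation 1.03, standardised effect 0.3, 90% power and two-sided 5%:

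- controls = ((1.960 + 1.282)/0.3)^2 x (1 + 1.07/1.03) = 238.0, and 238.0/0.9 = 264.5;
- intervention = 1.03 x 264.5 = 272.4;
- total 536.9, against the stated 535 (263 + 272).

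This only confirms the arm sizes. Nothing in the present point changes the power. SAP 2.8 gives 585 recruited and 15% loss. If the 1.03:1 ratio held and loss was equal by arm, controls = 585/2.03 = 288, and followed up = 288 x 0.85 = 245.

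**3. Controls not asked.** The share responding by telephone only is not in the documents. The assumed range is 10-20% of controls, counted among the 245.

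| Telephone-only share | Controls | Share of followed-up controls |
|---|---|---|
| 10% | 0.10 x 288 = 29 | 29/245 = 12% |
| 20% | 0.20 x 288 = 58 | 58/245 = 24% |

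**4. Effect on the reported percentage.** Suppose the 245 followed-up controls are the denominator and the telephone group contributes no events.

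- Equal risk: the control percentage is understated by 12-24%.
- Telephone group at twice the risk (assumed): 2 x 29/(2 x 29 + 216) = 21%, and 2 x 58/(2 x 58 + 187) = 38%.

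**5. Effect in counts.** With an assumed three-month SAE risk of 1-5%, participants with a missed event number from 29 x 0.01 = 0.3 to 58 x 0.05 = 2.9. Doubled risk in the telephone group gives 0.6 to 5.8.

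**6. What the call cannot recover.** About 288 x 0.15 = 43 controls are lost altogether. A question on the call does not reach them.

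**The case against.** The strongest reply has five parts.

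- **Other routes exist.** A reader might infer that the three-month enquiry is the control arm's only source of SAEs. The documents do not support that. Death is an SAE criterion, and Protocol 4.4 has deaths reported whenever they are identified, mostly from the GP records of 12-month non-responders. For those same non-responders, discharge letters would also reveal admissions, although no rule passes them to SAE reporting. The point is therefore limited to non-fatal events.
- **Not every non-responder goes unasked.** A reader might infer that any control who misses the online form is never asked. That is also too wide. The first chase call seeks completion of the whole form, and for participants not fluent in English the aim is to collect all outcomes, or as many as possible, verbally (Protocol 2.3.1).
- **Protocol 4.2.1 is unconditional.** It does not confine the enquiry to the online form, and the limit in 5.1 could be read as covering outcome measures only. This has some force: the text is ambiguous, and a missing tick does not override the narrative. But 4.2.3 ties the enquiry to the questionnaire, so the passages still need reconciling.
- **The call script is not available.** The data management plan and questionnaires are not among the documents, so an SAE prompt on the call cannot be ruled out. If one exists, the restriction in 5.1 is wrong as written.
- **The gap applies to both arms.** With similar telephone use, a table restricted to the three-month enquiry would under-count both arms alike. This stands. The asymmetry comes from the intervention arm's session-based capture, a choice that 4.2.1 explains.

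**Conclusion.** The point holds in a limited form. On the plan as written, a control participant who is fluent in English and reached only by the final call gives the primary outcome with no planned enquiry about non-fatal SAEs. The three-month enquiry is also absent from both schedules, and the SAP does not say who belongs in the SAE denominator.

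The documents do not fix the size. The 12-24% of followed-up controls rests on an assumed telephone share, on equal loss by arm, and on the 15% loss applying at three months. SAP 2.8 gives that 15% without arm or time point. The likely number of missed events is small, about 0.3 to 3 at the assumed SAE risks with equal risk, and up to about 6 if the telephone group has twice the risk. SAEs may be few in total, so even this could affect the comparison between arms. It does not invalidate the safety data, and it does not touch the primary efficacy analysis. It is worth correcting because the correction is cheap.

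**What to change.** - **Telephone call, both arms:** add the three-month SAE question to the core script, after the PROPr and EQ-5D-5L so that it cannot affect those answers. Amend Protocol 5.1 and 2.3.1 and SAP 2.6.2 to match.
- **Table 1, both documents:** add a separate SAE-enquiry row ticked at three months. The existing adverse-events tick can stay for the session-based log.
- **SAP section 6:** report the three-month SAE percentage by arm among participants who answered the SAE question by either route, and state how many in each arm were not asked.

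SAP 2.8 says recruitment is complete, so some three-month calls may already be past. For those, the denominator and the disclosure still apply.

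The cost is about a minute per call, one table row in each document and a short addition to the SAP. Positive answers bring a follow-up contact, an SAE form and the two causality assessments of Protocol 4.2.4, and the reported SAE count may rise.
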